4. SUBJECT POPULATION

Screening for eligible subjects will be performed within 28 days before administration of the study drug.

The inclusion and exclusion criteria for enrolling subjects in this study are described in the following 2 subsections. If there is a question about the inclusion or exclusion criteria below, the investigator must consult with the appropriate sponsor representative and resolve any issues before enrolling a subject in the study. Waivers are not allowed. Exceptional and limited retesting of abnormal screening values that lead to exclusion may be allowed after discussion and approval by the sponsor during the screening period (to reassess eligibility). This should only be considered if there is no anticipated impact on subject safety.

For a discussion of the statistical considerations of subject selection, refer to Section 11.2, Sample Size Determination.

4.1. Inclusion Criteria

Each potential subject must satisfy all of the following criteria to be enrolled in the study:

- 1. 1.1. Criterion Modified per Amendments 1 and 5
 - 1.2 Men or WONCBP, aged 18 to 70 years (inclusive). Note: Subjects should be at least 18 years of age or older as per the legal age of consent in the jurisdiction in which the study is taking place.

A WONCBP is defined as:

- Postmenopausal
 - A postmenopausal state is defined as no menses for 12 months without an alternative medical cause. A high follicle stimulating hormone (FSH) level (>40 IU/L or mIU/mL) in the postmenopausal range may be used to confirm a postmenopausal state in women not using hormonal contraception or hormonal replacement therapy.
- O Permanently sterile

 Permanent sterilization methods include hysterectomy, bilateral salpingectomy, bilateral tubal occlusion/ligation procedures, and bilateral oophorectomy.

If reproductive status is questionable, additional evaluation should be considered.

- 2. 2.1 Criterion Modified per Amendments 1, 2, and 5
 - 2.3 Meet DSM-5 diagnostic criteria for MDD, without psychotic features (DSM-5 296.22, 296.23, 296.32, or 296.33), based upon clinical assessment and confirmed by the SCID-CT. In addition, their major depressive episode must be deemed "valid" using the SSQ interview administered by remote, independent raters. The length of the current depressive episode must be ≤18 months.
- 3. 3.1 Criterion Modified per Amendments 1, 3, and 5
 - 3.3 Have had an inadequate response to at least 1 but no more than 3 antidepressants (see the inclusion criterion below), administered at an adequate dose and duration in the current episode of depression, as measured by the MGH-ATRQ. An inadequate response is defined as <50% reduction in depressive symptom severity, as assessed by the MGH-ATRQ. An adequate trial is defined as an antidepressant treatment for at least 4 weeks at or above the minimum therapeutic dose specified in the MGH-ATRQ, for any particular antidepressant. The inadequate response must include the subject's current antidepressant treatment.
- 4. 4.1 Criterion Modified per Amendments 1, 2, 3, and 5
 - 4.4 Is receiving monotherapy treatment for depressive symptoms with one of the following SSRI/SNRI antidepressants, in any formulation: citalopram, duloxetine, escitalopram, fluvoxamine, fluoxetine, milnacipran, levomilnacipran, paroxetine, sertraline, venlafaxine, desvenlafaxine, vilazodone, or vortioxetine at a stable dose (at or above the minimum therapeutic dose level) for at least 4 weeks, and for no

greater than 12 months, at screening. Modification of an effective preexisting therapy should not be made for the explicit purpose of entering a subject into the study.

Note: Dose and duration of treatment should be verified by the investigator using the medical or pharmacy records. The investigator will use this information to complete the MGH-ATRQ, which will then be corroborated by the independent rater.

- 5. 5.1 Criterion Modified per Amendments 1 and 3
 - 5.2 Have a MADRS total score ≥25 (performed by independent, centralized remote raters) at screening and must not demonstrate a clinically significant improvement (ie, an improvement of >20% on their MADRS total score) from the screening to baseline visit.
- 6. Criterion Modified per Amendment 3
 - 6.1 Body mass index (BMI) between 18 and 35 kg/m² inclusive (BMI=weight/height²).
- 7. Must be an outpatient at screening.
- 8. Criterion Modified per Amendment 3
 - 8.1 Must be otherwise healthy on the basis of physical examination, medical history, vital signs, 12-lead ECG, and clinical laboratory tests performed at screening. If the results of the clinical laboratory tests are outside the normal reference ranges, the subject may be included only if the investigator judges the abnormalities or deviations from normal to be not clinically significant or to be appropriate and reasonable for the population under study. This determination must be recorded in the subject's source documents and initialed by the investigator.
- 9. 9.1 Criterion Modified per Amendments 2 and 3
 - 9.2 Must sign an informed consent form (ICF) indicating that he or she understands the purpose of and procedures required for the study and be willing to participate in the study.
- 10. Criterion Deleted per Amendment 5
- 11. Criterion Deleted per Amendment 5
- 12. Criterion Modified per Amendment 5
 - 12.1 A woman must agree not to donate eggs (ova, oocytes) for the purposes of assisted reproduction during the study and for a period of at least 1 month after receiving the last dose of study drug.

13. 13.1 Criterion Modified per Amendments 1 and 5

- 13.2 During the study and for a minimum of 1 spermatogenesis cycle (defined as approximately 3 months) after receiving the last dose of study drug, a man:
 - who is sexually active with a woman of childbearing potential must agree to use a barrier method of contraception (eg, condom with spermicidal foam/gel/film/cream/suppository)
 - who is sexually active with a woman who is pregnant must use a condom
 - must agree not to donate sperm.
- 14. Be willing and able to adhere to the prohibitions and restrictions specified in this protocol.
- 15. Must sign a separate informed consent form (or their legally-acceptable representative must sign) if he or she agrees to provide optional DNA samples for research (where local regulations permit). Refusal to give consent for the optional DNA research samples does not exclude a subject from participation in the study.

4.2. Exclusion Criteria

Any potential subject who meets any of the following criteria will be excluded from participating in the study:

- 1. 1.1 Criterion Modified per Amendments 3 and 5
 - 1.2 Has a history of, or current signs and symptoms of, severe renal insufficiency (creatinine clearance <30 mL/min); moderate to severe hepatic insufficiency (Child-Pugh Score 7-9), significant or unstable cardiovascular, respiratory, gastrointestinal, neurologic (including narcolepsy), hematologic, rheumatologic, immunologic or endocrine disorders (including uncontrolled hypo- or hyperthyroidism or diabetes, or insulin-dependent diabetes mellitus). Subjects with non-insulin dependent diabetes mellitus who are well-controlled (hemoglobin $A1_C$ [HbA1_C] \leq 7.5% and fasting glucose <126 mg/dL at screening) may be eligible to participate if otherwise medically healthy, and if on a stable regimen of glucose-lowering medications for at least 2 months prior to screening.
- 2. Criterion Modified per Amendment 1
 - 2.1 Has current signs/symptoms of hypothyroidism or hyperthyroidism (Subjects with known hypothyroidism who have been on stable treatment for at least 3 months prior to screening are required to have thyroid-stimulating hormone [TSH] and free thyroxine [FT₄] obtained. Any subject with an elevated TSH should also have FT₄ measured. In any case where the TSH value is out of range, but FT₄ is normal, the findings should be discussed directly with the medical monitor before the subject is enrolled. If the FT₄ value is out of range, the subject is not eligible. Subjects taking thyroid supplementation for antidepressant purposes are not allowed in the study).

3. Has signs and symptoms of Cushing's Disease, Addison's Disease, primary amenorrhea, or other evidence of significant medical disorders of the HPA axis.

4. Criterion Modified per Amendment 1

- 4.1 Has a current or recent history of serious suicidal ideation within the past 6 months, corresponding to a positive response on item 4 (active suicidal ideation with some intent to act, without specific plan) or item 5 (active suicidal ideation with specific plan and intent) for ideation on the C-SSRS, or a history of suicidal behavior within the past year, as validated by the C-SSRS at screening or Day 1. Subjects with a prior suicide attempt of any sort, or prior serious suicidal ideation/plan within the past 6 months, should be carefully screened for current suicidal ideation and only subjects with non-serious items (1-3 of the suicidal ideation section of the C-SSRS) may be included at the discretion of the investigator.
- 5. 5.1 Criterion Modified per Amendments 3 and 5
 - 5.2 Has a history of lack of response to to 3 or more adequate antidepressant treatments, as indicated by no or minimal (≤25% improvement in symptoms) when treated with an antidepressant of adequate dose (per MGH-ATRQ) and duration (at least 4 weeks).
- 6. Has a history or evidence of noncompliance with current antidepressant therapy.
- 7. 7.1 Criterion Modified per Amendments 1 and 3
 - 7.2 Has taken a known moderate or strong inhibitor/inducer of CYP3A4 and CYP2C9 or a dual inhibitor/inducer of CYP3A4 and CYP2C9 within 14 days (or after washout ie, duration of 5 times the drug's half-life) before the first study drug administration on Day 1. See Attachment 1 for examples of moderate and strong inhibitor/inducer of CYP3A4 and CYP2C9 or a dual inhibitor of CYP3A4 and CYP2C9
- 8. Criterion Modified per Amendment 1
 - 8.1 Has a primary DSM-5 diagnosis of panic disorder, generalized anxiety disorder, social anxiety disorder, or specific phobia which has been the primary focus of psychiatric treatment within the past 2 years. Current or lifetime history of obsessive-compulsive disorder, posttraumatic stress disorder, anorexia nervosa, or bulimia nervosa is exclusionary.
- 9. Criterion Modified per Amendment 3
 - 9.1 Has history or current diagnosis of a psychotic disorder, bipolar disorder, mental retardation, autism spectrum disorder, or borderline personality disorder, somatoform disorders, chronic fatigue syndrome or fibromyalgia.
- 10. Has any significant primary sleep disorder, including but not limited to obstructive sleep apnea, restless leg syndrome, or parasomnias.

11. Criterion Modified per Amendment 3

- 11.1 Has significant hypersomnia that is not related to insomnia disorder (based on clinical judgment of the investigator).
- 12. Is a night-shift worker.
- 13. Has a history of substance or alcohol use disorder according to DSM-5 criteria within 6 months before screening or positive test result(s) for alcohol and/or drugs of abuse (opiates [including methadone], cocaine, amphetamines, methamphetamines, cannabinoids, barbiturates, 3,4-Methylenedioxymethamphetamine [XTC] and benzodiazepines) at screening or at baseline.
- 14. Had a clinically significant acute illness within 7 days before the first dose of study drug.
- 15. Criterion Deleted per Amendment 3.
- 16. Has a known malignancy or history of malignancy within 5 years before screening (exceptions are squamous and basal cell carcinomas of the skin and carcinoma in situ of the cervix, or malignancy that in the opinion of the investigator, with concurrence with the sponsor's medical monitor, is considered cured with minimal risk of recurrence).
- 17. 17.1 Criterion Modified per Amendments 1 and 3
 - 17.2 Has clinically significant ECG abnormalities at screening or Day 1 prior to randomization defined as:
 - QT interval corrected according to Fridericia's formula (QTcF): ≥450 msec (males); ≥470 msec (females)
 - Evidence of 2nd and 3rd degree atrioventricular block, or 1st degree atrioventricular block with PR interval >200 msec, left bundle branch block (LBBB).
 - At screening, history of additional risk factors for torsades des pointes (eg, heart failure, hypokalemia, family history of long QT syndrome, or the use of concomitant medications that prolong the QT/QTc interval)
 - Features of new ischemia
 - Valvular heart disease including mitral regurgitation and aortic stenosis
 - Other clinically important arrhythmia.

Note: Subjects with right bundle branch block (RBBB) may be allowed provided confirmation that RBBB is not associated with underlying cardiac/lung diseases.

- 18. Previous exposure to the study drug, JNJ-42847922.
- 19. Criterion Deleted per Amendment 3.
- 20. Criterion Modified per Amendment 3

- 20.1 Has received any prior treatment with electroconvulsive therapy, vagal nerve stimulation, a deep brain stimulation device, or transcranial magnetic stimulation.
- 21. Criterion Deleted per Amendment 3.
- 22. Ongoing psychological treatments (eg, Cognitive Behavior Therapy, Interpersonal Psychotherapy, Psychodynamic Psychotherapy etc.), initiated within 2 months prior to start of the double-blind treatment phase. A subject who has been receiving ongoing psychological treatment for a period of greater than 2 months is eligible, if the investigator deems the psychological treatment to be of stable duration and frequency.
- 23. Criterion Modified per Amendment 3
 - 23.1 Has known allergies, hypersensitivity, intolerance or any contraindication to JNJ-42847922 or its excipients (refer to Investigator's Brochure for JNJ-42847922).
- 24. Criterion Deleted per Amendment 1.
- 25. Donation of 1 or more units (approximately 450 mL) of blood or acute loss of an equivalent amount of blood within 60 days before the first dose of study drug.
- 26. Has cognitive impairment that would render the informed consent invalid, or limit the ability of the subject to comply with the study requirements.
- 27. Has any condition for which, in the opinion of the investigator, participation would not be in the best interest of the subject (eg, compromise the well-being) or that could prevent, limit, or confound the protocol-specified assessments.
- 28. Has taken any disallowed therapies as noted in Section 8, Prestudy and Concomitant Therapy before the planned first dose of study drug.
- 29. Has received an investigational drug (including investigational vaccines) or used an invasive investigational medical device within 3 months before the planned first dose of study drug or is currently enrolled in an investigational study.
- 30. Criterion Modified per Amendment 5
 - 30.1 Is pregnant, or breastfeeding, while enrolled in this study or within 1 month after the last dose of study drug.
- 31. Has plans to father a child while enrolled in this study or within 3 months after the last dose of study drug.
- 32. Has had major surgery, (eg, requiring general anesthesia) within 2 weeks before screening, or will not have fully recovered from surgery, or has surgery planned during the time the subject is expected to participate in the study.

Note: Subjects with planned surgical procedures to be conducted under local anesthesia

may participate.

33. Employee of the investigator or study site, with direct involvement in the proposed study or other studies under the direction of that investigator or study site, as well as family members of the employees or the investigator.

NOTE: Investigators should ensure that all study enrollment criteria have been met at screening. If a subject's clinical status changes significantly (including any available laboratory results or receipt of additional medical records) after screening but before the first dose of study drug is given such that he or she no longer meets all eligibility criteria, then the subject should be excluded from participation in the study. Section 17.4, Source Documentation, describes the required documentation to support meeting the enrollment criteria.

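### Exclusion criterion 4.1 both excludes and permits subjects with C-SSRS item 4-5 ideation in the past 6 months whose current ideation is only items 1-3

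*Protocol*

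**What the plan says.** Criterion 4.1 in Protocol Section 4.2 opens with the exclusion: "Has a current or recent history of serious suicidal ideation within the past 6 months, corresponding to a positive response on item 4" or item 5. A second limb follows: "or a history of suicidal behavior within the past year, as validated by the C-SSRS at screening or Day 1".

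The next sentence returns to subjects with a history: "Subjects with a prior suicide attempt of any sort, or prior serious suicidal ideation/plan within the past 6 months, should be carefully screened" for current ideation. It ends: "only subjects with non-serious items (1-3 of the suicidal ideation section of the C-SSRS) may be included at the discretion of the investigator".

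Three general rules bear on how these are read. The lead-in to Section 4.2 says: "Any potential subject who meets any of the following criteria will be excluded from participating in the study". Section 4 says "Waivers are not allowed", and for any question about a criterion it says that "the investigator must consult with the appropriate sponsor representative and resolve any issues before enrolling a subject in the study".

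Section 1.3 lists the exclusion of high-risk subjects under Section 4.2 among the measures that reduce suicide risk in this trial.

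**The concern.** The criterion ties serious ideation to items 4 and 5 and non-serious ideation to items 1 to 3, and both sentences use the same 6-month window. The first sentence tests history over those 6 months. The second takes subjects with that history, tests only their present state, and allows entry if the present state is milder. For someone whose serious ideation has eased within the window, the two tests give opposite results.

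At stake is whether a suicide-risk entry rule is applied in the same way everywhere. SAP Section 2.6 lists sites in seven countries (five in Europe, plus the US and Japan). An investigator who takes the second sentence as an exception could randomise a subject whom an investigator following the first would turn away.

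**Working it through.** No arithmetic applies. The check is to put each kind of subject through both sentences.

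| History | Ideation now | First sentence | Second sentence | Result |
|---|---|---|---|---|
| Item 4-5 within 6 months | Items 4-5 | Excludes | Does not admit | Agree |
| Item 4-5 within 6 months | Items 1-3 | Excludes | May be included | **Conflict** |
| Item 4-5 within 6 months | None | Excludes | Not named | Conflict only if no ideation counts as non-serious |
| Item 4-5 more than 6 months ago | None or items 1-3 | Does not exclude | Not named | No conflict |
| Attempt more than 1 year ago | Items 1-3 | Does not exclude | May be included | No conflict |
| Attempt within 1 year | Items 1-3 | Excludes | Covered literally, as no window is given | Reconcilable: read the second sentence as older attempts |

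The table shows where the conflict lies. It says nothing about how often it would arise, and its rows should not be counted as a measure of size.

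**Which sentence governs?** The lead-in and the no-waiver rule point to the first. Neither settles it, because a permission written into a criterion is not a waiver of that criterion. I found no statement elsewhere in the protocol or SAP that ranks the two.

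**What follows on each reading?** If the first governs, the ideation clause of the second has no effect for a true item 4-5 history, since everyone with that history in the window is already out. If the second is an exception, a subject with item 4 or 5 ideation in the past 6 months can enter once current ideation has eased to items 1-3.

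**Do other criteria show the intended form?** Only in part.

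- In criterion 1.2, well-controlled non-insulin-dependent diabetics "may be eligible to participate if otherwise medically healthy". They lie outside the excluded group, which is uncontrolled or insulin-dependent diabetes.
- Criterion 22 uses complementary windows on either side of 2 months of psychological treatment.
- Criterion 16 excludes malignancy within 5 years and then admits some of those same subjects, but it labels them as exceptions.

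So an exception inside the excluded group is a form that Section 4.2 uses. Criterion 4.1 has no such label, which leaves both readings open.

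**The case against.** The strongest reply is that this is an ambiguity with an obvious default. Meeting any criterion excludes, waivers are barred, and the second sentence is worded as a restriction, so a careful investigator would exclude. One in doubt must consult the sponsor before enrolling. Other safeguards remain: exclusion 27 covers any condition that makes participation contrary to the subject's interest, the C-SSRS is done at every site visit, and Section 10.2 discontinues treatment on the investigator's safety judgment or for acute ideation with a clear plan.

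Most of this stands, and it limits the harm. It does not remove the conflict. The consultation rule works only if the investigator sees a question, and a reader who takes the second sentence as permission sees none. The plan-based stopping rule also would not by itself catch a return to item 4, which is intent without a specific plan; that would rest on general safety judgment.

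A second reply concerns the qualifier about C-SSRS validation at screening or Day 1. Whether it reaches the ideation limb is arguable. Even if it does, what is validated is still a 6-month history.

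A third reply limits the claim. A reader might infer that, with the first sentence governing, the ideation clause of the second is wholly empty. The documents do not establish that. The clause also mentions a plan, and by the item labels in SAP Section 6.5.1 a plan without intent is neither item 4 (intent, no specific plan) nor item 5 (plan and intent). The clause may therefore reach some subjects whom the first sentence does not.

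**Conclusion.** The conflict is real and narrow. It affects subjects with item 4-5 ideation in the past 6 months whose current ideation is limited to items 1-3. The better default is that the first sentence governs, but the text does not say so. This rests on reading serious ideation in the second sentence as the items 4-5 that the first sentence ties it to.

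The documents give no count of such subjects, and none is estimated. The consequence is possible inconsistency between sites in a safety criterion.

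Three stronger conclusions are not supported:

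- A reader might infer that subjects with item 4-5 ideation at entry could be enrolled. Neither sentence admits them.
- A reader might infer that the rule on suicide attempts contradicts itself in the same way. It can be reconciled: attempts within 1 year are excluded and older ones are left to discretion.
- A reader might infer an effect on the efficacy conclusion. The primary analysis uses all randomised and dosed subjects, whatever their eligibility. Under SAP Section 5.2.3.2, a sensitivity MMRM drops subjects with major deviations that may affect efficacy, including entry without meeting criteria, so an affected subject's classification there could depend on the reading. No effect on the primary analysis, estimand or power is claimed.

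**What to change.** Make the first sentence govern without adding an eligibility condition. Either of two edits does this:

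1. Open the second sentence with *Subjects not excluded by the preceding sentence who have*, and leave the rest as it is. This keeps careful screening for anyone whom the clause reaches and the first sentence does not, such as a recent plan without intent.
2. Delete from the second sentence the clause on serious ideation or plan in the past 6 months. This is shorter, but it drops the careful-screening step for that possible remainder.

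I prefer the first. Either is an edit to one sentence and needs no extra visits, data or subjects. It should be made by protocol amendment with ethics approval under Section 17.1. Until then, sites should take questions about this group to the sponsor before enrolment, as Section 4 already requires.

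Moving the second sentence's window to ideation more than 6 months ago would also remove the conflict, but it would place a new condition on subjects whom the criterion does not now address. That is a separate choice for the sponsor and not part of this correction.
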